6. THE ANALYSES

6.1. Primary analysis (direct protection against severe and non-severe cholera)

This primary analysis will compare subjects according to the study agent actually received and will include only those subjects who satisfied the inclusion/exclusion criteria, followed the protocol, and received one complete dose.

Onset of follow-up for counting events: All cholera episodes will be included if they have onsets between 7 and 180 days after the zero time.

Direct protection is estimated by comparing the incidence of cholera among vaccine recipients and the incidence of the cholera among placebo recipients.

Numerator events for analysis: Numerator events will be cholera episodes (defined above) whose onsets are between 7 and 180 days after the zero time. Cholera cases that occur between the zero time and the beginning of follow-up (zero time +7 days) will not be considered as a cholera episode and will not be included in this analysis.

Denominator for analysis: Subjects in the denominator for analysis are those who completely ingested dose of the agent and were at least 12 months of age at zero time and were otherwise eligible and were noted as having received either oral cholera vaccine or placebo. In analyses of time-to-event, the person-time at risk begins at the zero time and continues until the date of death, date of out-migration, date of event under analysis, or to zero time +180 days for this analysis.

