The agent to be received by the participants will be determined by the randomization number on the vial. Vials will be consecutively numbered, but individually randomized into the vaccine or placebo arm. After shaking the vial properly, it will be opened and given to the participant. The contents will be poured into the mouth by the recipient, followed by intake of a small volume of water. We shall allow the participant to take the study agent by themselves for those who are 5 years and older. For younger children, the vaccine will be given by the vaccinator. At the time of the dosing, completeness of dosing will be observed and this information will be documented. Vials used for the administration of the vaccine and placebo will be disposed by incineration. The records of the vaccine and placebo usage and destruction will be maintained in the study file and also shared with the manufacturer for reconciliation.

Selection and Withdrawal of Participants

Inclusion criteria:

All healthy, consenting, non-pregnant (as ascertained by history) residents of a high risk group, at least 1 year of age, of the study area will be included in the trial.

Exclusion criteria:

The following will be excluded from the trial:

- Pregnant women (identified through verbal screening);
- Aged less than 1 year
- History of intake of any cholera vaccine

Participants may withdraw from the study at any point. The data collected for withdrawn participants, in addition to standard questionnaire data, will include the reason for withdrawal. No additional follow-up is envisioned for withdrawn participants.

Accountability procedures for the investigational product, including the comparator:

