In order to safeguard against bias, we will employ a randomization scheme. Blinding will be achieved in this trial by masking the identity of the agents by using randomization number codes for the vaccines and the placebos. After consenting and screening, eligible participants will receive investigational product in a sequential manner. The identity of the codes will be known to the statistician of IVI, who will otherwise not be involved in the study, the staff at Shantha, who will provide the study vaccine, and the staff at Bilcare, who will provide nonbiologic placebo and label all study agent vials before shipment to icddr, b. Study participants will be randomized to intervention or placebo group based on the randomization number of the study agent they will receive at the study site. Each vial will, in addition, contain a detachable sticker with the randomization number and study code on it. This will be used to label the vaccine register alongside the participant study ID during the vaccination in order to minimize transcription error in the vaccine register. The identity of the randomization numbers (in sealed envelopes) will be provided to the Data and Safety Monitoring Board (DSMB) and the on-site principal investigator. The safety monitor(s) of the study will have access to the list when needed.

Data and Safety Monitoring Board (DSMB)

The DSMB will be formed by the ERC of the icddr,b and will constitute members of the ERC as well as relevant experts in the field from Bangladesh and externally. The DSMB will hold meetings with the investigators of the study in the beginning and at regular intervals for study updates. Adverse events will be reported, to the DSMB. Members will visit the study site as needed. They will evaluate trial conduct and compliance with the protocol, the standard operating procedures, Good Clinical Practice, and the applicable regulatory requirements. The results of the study will be shared with DSMB for review. The DSMB will periodically review and evaluate the accumulated study data for safety, study-related adverse events, study conduct, completeness, timeliness, and protocol violation.

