5. OTHER DEFINITIONS

Zero time: The date of dose for the dose recipients and the start date of the mass vaccination (January 10, 2014) for non-dose recipients.

Complete dose recipients: Individuals who drank and swallowed one complete dose (the full course).

Incomplete dose recipients: Individuals who swallowed any amount of dose but not completed the full course.

No-dose recipients: Individuals who were present at zero time but not dosed. During routine demographic updates, individuals were identified as entered into the population prior to dosing and therefore would have been eligible at the time of vaccination. These individuals are also considered as the no-dose recipients.

Two-dose recipients: Individuals found to have taken two doses based on the vaccine record book.

Lost to follow up: Individuals who died or moved out of the study area from the resident any time after zero time. Note that internal migration out demographic events will not be considered as lost to follow-up.

Duration of follow up period: The time between 7 and 180 days after the zero time.

Pre-dosing period: The period on or before the zero time. Events whose onsets occur in this period will not be considered in the analysis.

Post dose interval: The interval between the zero time and 7 days from zero time. Cholera events whose onsets occur in this period will not be considered in the analysis.

Post follow up period: The time after the completion of the follow up period. Events whose onsets occur in this period will not be considered in the analysis.

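### SAP efficacy analyses keep only eligible, protocol-following, complete-dose recipients by agent received, and no stated estimate covers everyone dosed by randomised vial

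*Supplement*

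**What the plan says.** SAP section 6.1 sets the primary comparison: "This primary analysis will compare subjects according to the study agent actually received and will include only those subjects who satisfied" the entry criteria, "followed the protocol, and received one complete dose". Its denominator repeats the restriction: "Subjects in the denominator for analysis are those who completely ingested dose of the agent and were at least 12 months of age". Section 6.2, on severely dehydrated cholera, uses the same denominator. Section 9 (Statistical methods) adds no other population.

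SAP section 5 defines two groups outside that set. Incomplete-dose recipients are "Individuals who swallowed any amount of dose but not completed the full course". Two-dose recipients are "Individuals found to have taken two doses based on the vaccine record book". Section 6 mentions neither group by name. The adherence condition is not defined in the available text. Nor is the requirement in SAP section 2 that the dose be correct as well as complete.

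Allocation is described in the current protocol. Under *Administration of vaccine or placebo*: "Vials will be consecutively numbered, but individually randomized into the vaccine or placebo arm". Under *Maintenance of randomization number codes*: "After consenting and screening, eligible participants will receive investigational product in a sequential manner", and "Study participants will be randomized to intervention or placebo group based on the randomization number of the study agent they will receive" at the site.

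The protocol's *Assessment of Efficacy* also aims at a complete dose, although its primary endpoint mentions only receipt of one dose. The protocol's *Analysis plan* refers to assignment in one place only, for Kaplan-Meier curves that are described as descriptive.

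**The concern.** Once the vial is handed over, the arm is fixed. Whether the dose is fully swallowed, whether a second dose is taken and whether the protocol is judged to have been followed are settled afterwards. Excluding people on these grounds can unbalance the arms if the exclusions differ by arm and are linked to cholera risk.

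A difference by arm is possible but not shown. The agents are a killed whole-cell suspension and a starch, gum and dye placebo. The protocol describes the placebo as alike in nature and appearance and is silent on taste. Vaccinators feed the under-fives, the group in which incomplete swallowing is most plausible. The undefined adherence condition also leaves room for judgement about who counts.

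At stake is the ability to see whether this happened. With no all-dosed estimate by vial, a reader could not tell whether the complete-dose result owes anything to who was dropped.

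**Working it through.** **1. The plan's own figure.** Inputs from the protocol's sample-size section: placebo risk p2 = 0.00056 over six months, R = 0.50 (so p1 = 0.00028), R0 = 0.90, k = 0.50, one-sided alpha 0.05, power 0.80.

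N = (z_α + z_β)² [q1/(k p1) + q2/((1−k) p2)] / (log R0 − log R)² gives 191,659, against 191,660 stated. The figure is reproduced. At 95,830 per arm the expected events are 95,830 × 0.00056 = 53.7 on placebo and 95,830 × 0.00028 = 26.8 on vaccine, 80.5 in all. The standard error of the log hazard ratio is √(1/53.7 + 1/26.8) = 0.236, so at a hazard ratio (HR) of 0.50 the one-sided 95% upper bound is about 0.74.

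**2. Bias from one-sided exclusion.** Assume that an extra fraction f is dropped from the vaccine arm only, and that those dropped have r times the risk of those who remain. The risk in the retained vaccine set is then the whole-arm risk divided by (1 − f + f r), and

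apparent HR = true HR / (1 − f + f r).

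| f | r | Divisor | Apparent VE, true VE 0 | Apparent VE, true VE 50% |
|---|---|---|---|---|
| 1% | 2 | 1.01 | 1.0% | 50.5% |
| 2% | 3 | 1.04 | 3.8% | 51.9% |
| 5% | 3 | 1.10 | 9.1% | 54.5% |
| 10% | 5 | 1.40 | 28.6% | 64.3% |

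Neither f nor r comes from the documents. The last row is an extreme. On the log scale the middle rows shift the estimate by log 1.04 = 0.039 and log 1.10 = 0.095, against the standard error of 0.236. An excess in the placebo arm works the other way: at f = 2% and r = 3, a true VE of 50% would appear as 1 − 0.50 × 1.04 = 48.0%. Equal exclusion in both arms, with the same r, cancels.

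**3. Cost of an all-dosed analysis.** Assume that a fraction f of vaccinees is incompletely dosed, has average risk and gets no protection. Then VE = 50% × (1 − f). Power is taken at 191,660 evaluable and R0 = 0.90.

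| f | VE | Power |
|---|---|---|
| 0 | 50.0% | 80.0% |
| 1% | 49.5% | 79.0% |
| 2% | 49.0% | 78.0% |
| 5% | 47.5% | 74.9% |

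**The case against.** The strongest reply is that the arm is the number on a blinded vial given after consent and screening. Agent received and agent assigned then coincide, apart from labelling or recording errors and two-dose cases. This stands. A reader might infer from the as-received wording that the efficacy estimate has lost the protection of randomisation. The documents do not support that, because the design leaves almost no room for crossover.

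Several further points also stand:

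- Ineligibility that existed before dosing and is ascertained blind should be independent of arm. Removing such people should not bias the comparison, even when the fact emerges later, as it may at the pregnancy check two months after dosing.
- The protocol keeps age in the Cox model whatever the proportionality test shows, and age is a SAP candidate covariate. If exclusions differ by arm only through age, adjustment removes much of the bias. The figures in step 2 are crude.
- A taste difference is conjecture, since silence in the protocol is not evidence of one.
- Protocol and SAP both target one complete dose, so the choice of primary population is defensible.
- A reader might infer that this is the trial's only efficacy estimate. It is not: later time points, watery diarrhoea, and overall and total protection are also planned. None of them, however, states an as-randomised population.

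The absence can be confirmed only for the available text. The SAP overview and the CONSORT chart in Appendix 1 are not shown.

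What the reply does not meet is selection on incomplete ingestion within age groups, the unspecified handling of two-dose recipients, and the undefined adherence condition.

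**Conclusion.** The point holds as a gap in the plan. Efficacy is estimated in a set restricted after vial allocation, and no stated estimate covers everyone dosed by randomised vial. Randomisation is weakened rather than absent, and the exposure lies mainly in incomplete doses, two-dose recipients and the undefined adherence condition.

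The likely effect is small if these exclusions are few or balanced. The illustrative 3.8% to 9.1% at a true VE of 0 (51.9% to 54.5% at a true 50%) needs an assumed one-arm excess of 2% to 5%, an assumed threefold risk relative to those remaining, and no age adjustment.

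A reader might set the 9.1% beside the 10% margin implied by R0 = 0.90 and conclude that the trial's result is in jeopardy. That comparison applies only if the vaccine does nothing. At the planned VE of 50%, the same assumptions move the estimate by under five percentage points, against a planned upper bound near 0.74.

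**What to change.** - Pre-specify, and report beside the complete-dose analysis, a Cox analysis of everyone given any amount of study agent. Analyse by the arm of the first vial number, whatever the completeness of the dose, later-found ineligibility or a second dose, and count events from day 7. The complete-dose set can remain primary.
- Tabulate incomplete-dose, two-dose and other excluded recipients by arm and age group. Include anyone handed a numbered vial who swallowed none of it, since the added analysis would not contain them.
- Before unblinding, define what following the protocol and a correct dose mean for inclusion, and state how two-dose recipients are handled.

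The cost is SAP wording, one more model run and a table. Under the protocol, vial numbers are already recorded against participant IDs in the register and completeness of dosing is documented. The added estimate may be slightly diluted, for example from 50% to 49% if 2% of vaccinees were incompletely dosed and unprotected.

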6.2. Secondary analysis (direct protection against severely dehydrated cholera)

A severely dehydrating cholera episode, is defined by the presence of at least two of the following signs and symptoms: sunken eyes, dry tongue, thirsty, irritable condition, less active than usual, skin-pinch goes back slowly, low volume of radial pulse along with inability to drink, or uncountable or absence of radial pulse.

Onset of follow-up for counting events: Severely dehydrated cholera episodes will be included if they have onsets between 7 and 180 days after the zero time.

Direct protection is estimated by comparing the incidence of severely dehydrated cholera among vaccine recipients and the incidence of the severely dehydrated cholera among placebo recipients.

Numerator events for analysis: Numerator events will be severely dehydrated cholera episodes (defined above) whose onsets are between 7 and 180 days after the zero time. Cases that occur between the zero time and the beginning of follow-up (zero time +7 days) will not be considered as an episode and will not be included in this analysis.

Denominator for analysis: Subjects in the denominator for analysis are those who completely ingested dose of the agent and were at least 12 months of age at zero time and were otherwise eligible and were noted as having received either oral cholera vaccine or placebo. In analyses of time-to-event, the person-time at risk begins at the zero time and continues until the date of death, date of out-migration, date of event under analysis, or to zero time +180 days for this analysis.

7. CANDIDATE VARIABLES FOR COVARIATES

Candidate variables for inclusion as covariates in the final model are listed below. In this instance, the variables that will have p value <0.10 will be selected. The candidate variables are as follows:

- Individual level
 - Age at zero time
 - Gender
 - Had diarrhea in past 6 months at baseline census
- Household level
 - Number of member in the household
 - House ownership
 - Months living in the area
 - Source of drinking water
 - Type of drinking water
 - Sanitation status
 - Hand washing practices
 - Per-capita household expenditure
 - % of vaccinees within 100m around the household
- Spatial variables
 - Distance to the nearest health facility
 - Distance from the nearest ICVB intervention clusters
 - Improved sanitation coverage within 100m around the household
 - Safe water coverage within 100m around the household
 - Population density within 100m around the household
 - Mobility rate within 100m around the household. This is to be calculated as $(\text{migration in} + \text{migration out}) / \text{zero time population all ages} * 100$

8. SUBGROUP ANALYSIS

Age-specific protective efficacy will be estimated by

Age group:

Age at zero time

- 1-4.9 years
- 5-14.9 years
- 15 years +

Duration of follow-up:

- Zero time to 90 days
- 91 days to 180 days from zero time

[figure not shown]
9. STATISTICAL METHODS

The primary analysis will address occurrence of cholera during six months of follow-up among vaccine and recipients. Cox proportional hazard regression models will be used, verifying first that the proportionality assumption is satisfied for all independent variables. Hazard ratios (HRs) of the target outcome in the vaccine recipients versus placebo recipients will be estimated by exponentiating the coefficient for the vaccine variable in these models, and vaccine protection will be estimated as $[(1 - HR) \times 100\%]$. Standard errors for the coefficients will be used to calculate one-tailed p values and 95% upper confidence intervals for the HRs.

[figure not shown]
Final adjusted estimates will be obtained from models including the variables which will be found to be independently associated with the time to the event at p value $< .10$ in a backward selection algorithm.

To evaluate heterogeneity of vaccine protection among different subgroups, interaction terms between vaccination and subgroup variables in these models will be evaluated. P values and 95% confidence intervals for these analyses will be calculated as two-tailed.

[figure not shown]
Appendix1. CONSORT for assembling population for the primary analysis

[figure not shown]
[figure not shown]
Appendix2. Episode classification (primary endpoint)

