With the following assumptions:

- Incidence among placebo group, p_2 , = 0.56 cases/1000/six month
- Vaccine protective efficacy (1- R) = 50%
- Significance level (α) = 0.05 (one-tailed)
- Statistical power (1- β) = 0.80
- Proportion of the total sample from population 1 (k) = $n_1/N=0.50$, where $N=n_1+n_2$, n_1 and n_2 are the population sizes for vaccine and placebo arms, respectively.

The method with the above assumptions yielded 191,660 individuals required in the two arms of the study. Assuming 65% participation rate, attrition 25% annually (6.25% for the 6 month period) and excluding those <1

year (2%) and pregnant women (1%), a total of 324,178 population are required to be registered during population enumeration. Considering the attrition rate, at least 204,438 individuals are required to be vaccinated for this study.

Sample size required for immunogenicity endpoint

The sample size has been calculated with the assumption that it is important to evaluate whether the vaccine induces acceptable vibriocidal responses in relation to the placebo group. Based on an immunogenicity study of the whole-cell killed oral cholera vaccine in Kolkata (1 dose vs. 2 doses of Shanchol™) [19], we use the following assumptions:

For vibriocidal responses, defined as >4-fold increases between baseline and post-dosing in either Inaba or Ogawa antibodies, for each age group (less than 5 years, 5 to less than 15 years and 15 years or older), we assume 1) the background rate of responses in the placebo group will be 3% after the first dose and 2) the true rate of vibriocidal responses in the vaccine groups is 50%. At $p < 0.05$ (1-tailed), 0.8 power, to exclude a difference of seroconversion among vaccine and placebo recipients of 25% and a 20% drop-out, a total of 54 participants per group would be needed. We will require approximately 54 participants per arm per age group, for a total of 324 participants.

Procedures for reporting any deviation from the original statistical plan:

Additional analysis may be required, and will be conducted if agreed among by the investigators and will be initiated by the principal investigator.

Direct Access to Source Data/Documents

The investigator/institutions will permit (by way of written agreement) trial-related monitoring, audits, IRB/IEC review, and regulatory inspection, providing direct access to source data/documents.

Quality Control and Quality Assurance Procedures

Study Monitoring and Source Data Verification

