- Date of onset for first episode of watery diarrhea with severe dehydration detected in the study treatment centres from 7days to,6, 12,18and 24 months, respectively after dosing among those who received 1 dose of vaccine or placebo
- Date of onset for first episode of diarrhea with fecal excretion of *V. cholerae*O1 in non-participating subjects, who are detected within one of the study treatment centres from 7 daysup to 6,12,18and 24 monthsafter dosing of study participants.
- Date of onset for first episode of diarrhea with severe dehydration and fecal excretion of *V. cholerae*O1 in non-participating subjects, who are detected within one of the study treatment centres from 7 daysup to 6,12,18and 24 monthsafter dosing of study participants.

Secondary safety endpoints

- Number of adverse events and serious adverse events in participants who received 1 dose of vaccine or placebo and present for care of vaccine adverse effects at treatment settings or who die from the time of dosing until 28 days later (passive surveillance by type of complaint and by cause of death).

Secondary immunogenicity endpoints

- Geometric mean serum vibriocidal (to El Tor Inaba and Ogawa O1 serogroup organisms and to O139 serogroup organisms) titers measured in participants at baseline (day0) and 14 days after receipt of either vaccine or placebo.
- Four-fold or greater rises in titers of serum vibriocidal antibodies (to El Tor Inaba and Ogawa O1 serogroup organisms and to O139 serogroup organisms), relative to baselineday 0 and 14 two days after receipt of either vaccine or placebo

Analysis plan

To analyze vaccine protection, we will use Cox proportional hazard regression models verifying first that the proportionality assumption is satisfied for all independent variables. Checking of the proportional hazard assumption will be performed by plotting the observed standardized score with simulated realizations for each covariate in the model, and the p-value will be derived from the Kolmogorov-type supremum test based on 1,000 simulations. If a variable does not satisfy the proportionality assumption, then we will exclude the variable from the model. However, the critical variables such as vaccination status and age will be kept in the model irrespective of the results of the test for proportionality assumption.

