The outcome will be the time to event of the onset of the first episode of cholera. Hazard ratios (HRs) of the target outcome in the vaccine versus placebo groups will be estimated by exponentiating the coefficient for the vaccine variable (independent variable) in these models, and vaccine efficacy is estimated as $[(1 - \text{HR}) \times 100\%]$. Standard errors for the coefficients will be used to estimate P values and 95% confidence intervals for the HRs. Kaplan-Meier cumulative event free survival curves for patients assigned to vaccine and placebo groups will be prepared for descriptive purposes.

Simple analyses of vaccine impact will be performed. Final adjusted estimates will be obtained from models that included the covariates found to be independently associated with the time to the event at $P < 0.1$ in a backward selection algorithm. To evaluate heterogeneity of vaccine protection among different subgroups, we will evaluate interaction terms between the vaccination and subgroup variables in these models. The threshold for significance in the primary analysis will be set at $p < 0.05$ (one tailed) and 95% CIs (lower bound) will be calculated. In all other analyses, the threshold for significance will be set at $p < 0.05$ with two-tailed analysis.

Primary Analysis at 6 months of follow-up:

Primary analysis will be planned at 6 months following dosing. In addition, we will estimate the protective impact of vaccination against culture-proven *V. cholerae* O1 diarrhoea episodes severe enough to require treatment in a health care facility; age-specific protective efficacy; indirect and age-specific indirect vaccine protection using a GIS approach described elsewhere (Ali et al 2005); overall and age-specific overall and total vaccine protection; culture-proven *V. cholerae* associated with severe dehydration (the definition is in Appendix 12); and episodes of acute watery diarrhoea severe enough to require treatment in a health care facility; episodes of acute watery diarrhoea irrespective of severity. Seroconversion in the vaccine and control groups will also be compared. Statistical methods for these secondary analyses will be the same as those used in the primary analyses contingent on an adequate number of cases.

Analysis at 6,12,18 and 24 months of follow-up:

Primary analysis is to be performed at 6 months. The following available time points (12,18 and/or 24 months) will be for secondary analysis points.

Surveillance for 24 months

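### The plan produces a simple and a backward-selected adjusted vaccine efficacy and does not say which one decides the one-sided primary test

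*Supplement*

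**What the plan says.** **SAP.** Section 7 lists 18 candidate covariates for the final model and keeps those with p below 0.10. Section 9 states: "Final adjusted estimates will be obtained from models including the variables which will be found to be independently associated" with time to event, by backward elimination at the same threshold. One-tailed p values and upper confidence limits for the hazard ratio come from the Cox models of that section. The SAP text available mentions no simple or unadjusted estimate.

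**Protocol, Analysis plan.** This section adds a second estimate: "Simple analyses of vaccine impact will be performed". The backward-selected adjusted estimates follow. The primary threshold is then set at one-tailed 0.05, with no model attached to it.

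The same section holds the proportional-hazards rule: "If a variable does not satisfy the proportionality assumption, then we will exclude the variable from the model". The next sentence exempts critical variables and gives vaccination status and age as examples. A supremum test with 1,000 simulations is specified, but not the p value at which a variable fails.

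**One candidate without a time window.** SAP section 7 includes: "Mobility rate within 100m around the household. This is to be calculated as" the sum of in- and out-migration over the zero-time population, times 100. No period is given. SAP section 3 defines out-migration as occurring after zero time; it does not define the timing of in-migration.

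**The concern.** A one-sided primary test of a single hypothesis should rest on one estimate and one confidence bound that can be identified before the data are seen. Here two results are planned and neither is named as the test.

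One of the two has covariates chosen from the outcome data. Its standard errors are then used as if the model had been fixed beforehand. In an individually randomised trial this selection is not needed for validity, and the sample size formula did not rely on it for power.

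The two documents also treat age differently. The protocol protects age from the proportional-hazards rule. SAP section 7 lists it as an ordinary candidate that must reach p below 0.10, so the SAP does not guarantee that age stays in the final model.

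If the two results fell on opposite sides of the threshold, the plan would not say which one counts.

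**Working it through.** **Step 1: reproduce the plan's sample size.** Inputs are from the protocol's sample size section: placebo risk p2 = "0.56 cases/1000/six month", efficacy 50% (p1 = 0.00028, R = 0.50), null relative risk R0 = 0.90, one-tailed alpha 0.05, power 0.80, k = 0.50.

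N = (zα + zβ)² [q1/(k·p1) + q2/((1−k)·p2)] / (log R0 − log R)²

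- (1.645 + 0.842)² ≈ 6.183
- 0.99972/0.00014 + 0.99944/0.00028 ≈ 7,140.9 + 3,569.4 = 10,710.3
- (log 0.90 − log 0.50)² = 0.5878² ≈ 0.3455
- With unrounded inputs N = 191,659, against 191,660 stated.

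The formula compares two groups and contains no covariate term.

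**Step 2: expected cases at that N.**
- Placebo: 95,830 × 0.00056 = 53.7
- Vaccine: 95,830 × 0.00028 = 26.8
- Total: 80.5 (85.9 if all 204,438 to be vaccinated are counted)

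**Step 3: cases per candidate.** SAP section 7 has 3 individual, 9 household and 6 spatial variables, 18 in all. 80.5/18 = 4.5. The ratio is lower if a categorical candidate takes more than one degree of freedom.

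**Step 4: how far selection reflects chance.** If all 18 were independent noise, the expected number kept at p below 0.10 is 18 × 0.10 = 1.8. The chance of keeping at least one is 1 − 0.9^18 = 0.85.

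**Step 5: effect on the estimate.** Simulation at full N: 386 trials, true efficacy 50%, 18 covariates, of which five are prognostic with log hazard ratio 0.35 each (an assumption), arm forced into the model. Backward-selected minus unadjusted efficacy:
- mean difference 0.0 points, SD 0.25, largest 1.0
- decision on whether the upper bound lies below 0.90: never changed

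Stronger covariates matter more. With log hazard ratio 0.7 each, a small full-N check (30–40 trials per setting) gave mean absolute differences of 0.64 points at a true hazard ratio of 0.5 and 1.65 at 1.

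**Step 6: effect on type I error.** Simulation at true hazard ratio 1, 1,500 trials per row, one-sided 0.05. It used a reduced sample of non-cases, which exaggerates chance imbalance between arms:

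| Prognostic covariates | Unadjusted | Selected | Either |
|---|---|---|---|
| None | 4.1% | 4.1% | 4.3% |
| Five | 5.1% | 5.7% | 6.1% |

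Monte Carlo error is about √(0.05 × 0.95/1,500) = 0.6 points. With the same reduced sample, five prognostic covariates and a true hazard ratio of 0.5, the two models disagreed on the 0.90 criterion in 4.3% of trials. The full-N run showed no disagreement.

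The simulations use independent covariates with one degree of freedom each and approximate the Cox model by a rare-event regression. They do not model the proportional-hazards exclusion.

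**The case against.** The strongest defence is that little is left open. The candidates, the threshold, the algorithm, the proportionality check and the definition of efficacy are all written down. Calling the adjusted estimates final leans towards them as the headline. The SAP alone offers no competing estimate; the simple analysis appears only in the protocol. Figures next to the SAP's methods text are not in the text available, so its silence should be read with some caution. All of this stands, but leaning towards a model is not naming it, and the protocol's one-tailed threshold is attached to neither.

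The second defence is size. A low number of cases per candidate is a warning for building a prognostic model. It says much less about a randomised arm effect that stays in the model with about 95,000 people per arm. This also stands.

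Three stronger readings are tempting, and the documents do not support them:
- **The primary efficacy is biased or the type I error materially inflated.** Steps 5 and 6 do not show this.
- **The exclusion rule could remove age or the arm.** The protocol expressly spares both.
- **The mobility rate is a follow-up variable by definition.** Only out-migration is defined as after zero time. The census began in July 2012 with regular updates, so a baseline window is possible. What can be said is that the window is not stated. Nor is there an evident route by which a neighbourhood rate would differ by arm under blinded individual randomisation.

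**Conclusion.** The point holds as a gap in pre-specification. Two primary results are possible, the covariates of one are settled by the outcome data, and neither document says which decides.

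The consequence is small. Efficacy moves by about one point or less at full N under moderate assumed covariate effects, and somewhat more if covariates are strong and the vaccine has no effect. Under the null, counting either result as success rejected in 6.1% of trials against 5.1% for the unadjusted test alone, in a setting that overstates the difference.

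This rests on about 80 expected cases, which is a planning figure and not an observed count, and on the simulation assumptions above. It is worth correcting because the correction is nearly free.

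**What to change.** In SAP section 9 and the protocol's Analysis plan, name one primary model fixed in advance: Cox regression with vaccine arm, adjusted for or stratified by the SAP age groups 1–4.9, 5–14.9 and 15 years and over. State that its one-tailed p value and upper bound decide the primary hypothesis. Label the backward-selected model a sensitivity analysis, and give the simple analysis a stated supportive role.

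In the sensitivity model, compute the mobility rate from migration before zero time, or drop it.

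The exclusion rule then affects only the sensitivity model. Replacing it by stratifying the baseline hazard on every failing covariate is not advised: several candidates are continuous with no cut-points given, and about 80 cases would be spread over sparse strata.

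The cost is wording. N is unchanged because 191,660 comes from a formula without covariates, and every planned model is still run. The headline estimate gives up any small precision gain from the other covariates.
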